2.6 Interim Analysis

An interim analysis will be performed when the month 12 visit is completed for all the subjects (main study phase).

2.7 Determination of Sample Size

There are no available clinical data for Sculptra studied under conditions similar to the current study. However, based on what is seen in clinical studies of injectable fillers in the facial areas, it is

 GALDERMA	<small>Title</small> 43CHSA1803 Statistical Analysis Plan - Sculptra China	<small>Doc id</small> MA-40407
---	--	--

2019-10-24 08:59

Effective date:

Effective

reasonable to assume a response rate of at least 60% in the Sculptra Treatment Group at Month 12. For the no treatment Control Group, response rate of 25.8% has been observed in an ongoing clinical trial in China. Based on this, it was assumed that the response rate will be maximum 30% in the no-treatment Control Group at Month 12.

With a sample size of 100 subjects treated with Sculptra and 50 subjects in the no-treatment control group, Fisher's Exact test will have approximately 90% power to detect difference between the anticipated percentage of responders at a 5% significance level (two-sided). To account for 20% drop-outs, approximately 126 will be randomized to the Sculptra group and approximately 63 to the control group.

2.8 Changes in the Analysis Planned in the Protocol

Version: 1.0

 GALDERMA	Title 43CHSA1803 Statistical Analysis Plan - Sculptra China	Doc id MA-40407
--	---	---------------------------

Effective date: 2019-10-24 08:59

Effective date:

Effective

Version: 1.0

3 Planned Tables and Figures

Group B:

Table 3-1 Analysis populations, by site

Site	Subject Id	Safety		FAS		PP	
		n	%	n	%	n	%
Site 1							
Site 2							
...							
Total (N)							

$\% = (n/N) * 100$

Table 3-2 Group A, by site

Site	Subject Id	Group A	
		n	%
Site 1			
Site 2			
...			
Total (N)			

$\% = (n/N) * 100$

	Title 43CHSA1803 Statistical Analysis Plan - Sculptra China	Doc id MA-40407
--	---	---------------------------

Effective date: 2019-10-24 08:59

Effective

Version: 1.0

Table 3-3 – Subject disposition, Group B

Number of subjects		Sculptra	Control	Total
Screened		-	-	
Screening failures		-	-	
Randomized				
Treated			-	
Completed primary endpoint				
Completed				
Withdrawn				
Reason for withdrawal	Withdrawn consent			
	Lost to follow-up			
	Medical reason			
	Other			

% screening failures is based on total number of screened subjects.

In all other cases: % is based on the number of randomized subjects in each treatment group

Table 3-4 – Subject disposition, Group A

Number of subjects		Group A
Treated		
Completed		
Withdrawn		
Reason for withdrawal	Withdrawn consent	
	Lost to follow-up	
	Medical reason	
	Other	

2019-10-24 08:59

Effective date:

Effective

Version: 1.0

Table 3-5 Subject accountability, Group B

Number of subjects	Sculptra				Control			
	Expected	Performed	Missed	Withdrawn	Expected	Performed	Missed	Withdrawn
Baseline / Treatment 1								
Treatment 2 (optional)								
Treatment 3 (optional)								
Treatment 4 (optional)								
Week 5 after last treatment								
Month 6 after baseline								
Month 9 after baseline								
Month 12 after baseline								
Month 18 after baseline								
Month 24 after baseline								

Note: The main study consists of visits up to 12 months

Table 3-6 Subject accountability, Group A

Number of subjects	Expected	Performed	Missed	Withdrawn
Baseline / Treatment 1				
Treatment 2 (optional)				
Treatment 3 (optional)				
Treatment 4 (optional)				
Week 5 after last treatment				
Month 6 after baseline				
Month 9 after baseline				
Month 12 after baseline				
Month 18 after baseline				
Month 24 after baseline				

Note: The main study consists of visits up to 12 months

	Title 43CHSA1803 Statistical Analysis Plan - Sculptra China	Doc id MA-40407
---	---	---------------------------

2019-10-24 08:59

Effective date:

Effective

Version: 1.0

Table 3-7 Withdrawals, Group B

Subject Number	Treatment/Control	Date of withdrawal	Reason for withdrawal	Last visit	Date of last visit

Table 3-8 Withdrawals, Group A

Subject Number	Date of withdrawal	Reason for withdrawal	Last visit	Date of last visit

Table 3-9 – Protocol deviations affecting Per Protocol population (PP)

Protocol deviation	Subject Number(s)	Number of deviations

Table 3-10 – Protocol deviations not affecting Per Protocol population (PP), Group B

Protocol deviation	Number of subjects

Table 3-11 – Protocol deviations, Group A

Protocol deviation	Number of subjects

	Title 43CHSA1803 Statistical Analysis Plan - Sculptra China	Doc id MA-40407
--	---	---------------------------

2019-10-24 08:59

Effective date:

Effective

Version: 1.0

Group B**Table 3-12 Summary of demographics and baseline characteristics, FAS**

Characteristics	Parameter	Group B		
		Sculptra	Control	Total
Age (years)	n			
	Mean (SD)			
	Median			
	Range			
Gender				
Female	n (%)			
Male	n (%)			
Total	N			
Ethnic origin				
Han Chinese	n (%)			
Other ¹⁾	n (%)			
Total	N			
Baseline BMI	n			
	Mean (SD)			
	Median			
	Range			
MMVS Blinded	Right side			
	Score 2	n (%)		
	Score 3	n (%)		
	Score 4	n (%)		
	Total	N		
MMVS Blinded	Left side			
	Score 2	n (%)		
	Score 3	n (%)		
	Score 4	n (%)		
	Total	N		

	Title 43CHSA1803 Statistical Analysis Plan - Sculptra China	Doc id MA-40407
--	---	---------------------------

Table 3-13: Subjects reporting medical history/concurrent diseases and number of conditions by MedDRA System Organ Class (SOC), FAS

Primary SOC	Sculptra N = XX						Control N = XX					
	Total		Whereof ongoing at study start				Total		Whereof ongoing at study start			
	Subjects		Number of conditions	Subjects		Number of conditions	Subjects		Number of conditions	Subjects		Number of conditions
	n	%		n	%		n	%		n	%	
Vascular disorders												
Total												

 $\% = (n/N) * 100$

Note: A single subject may have reported medical history/concurrent diseases by more than one primary SOC category

Table 3-14: Prior use of facial fillers or implants, FAS

	Sculptra N = XX				Control N = XX			
	Subjects		Number of procedures	Subjects		Number of procedures		
	n	%		n	%		n	%
Total								

 $\% = (n/N) * 100$

Note: A single subject may have had several fillers or implants

Table 3-15: Prior use of other facial dermatological procedures, FAS

	Sculptra N = XX			Control N = XX		
	Subjects		Number of procedures	Subjects		Number of procedures
	n	%		n	%	
Total						

$\% = (n/N) * 100$

Note: A single subject may have had several facial dermatological procedures

2019-10-24 08:59

Effective date:

Effective

Version: 1.0

**Table 3-16: Subjects reporting concomitant medication, FAS**

	Sculptra N = XX				Control N = XX			
	No		Yes		No		Yes	
	n	%	n	%	n	%	n	%
Ongoing at study start								
Initiated during study								
Total								

 $\% = (n/N)*100$

Note: A single subject might have had concomitant medication ongoing at study start and initiated during study

Table 3-17: Subjects reporting concomitant medication and number of medications by reason, FAS

Reason for concomitant medication	Sculptra N = XX				Control N = XX			
	Subjects		Number of medications		Subjects		Number of medications	
	n	%	Total	Ongoing at study end	n	%	Total	Ongoing at study end
Related Adverse Event								
Unrelated Adverse Event								
Medical History								
Other								
Total								

 $\% = (n/N)*100$

Note: A single subject might have reported concomitant medication for several reasons

Table 3-18: Subjects reporting concomitant medication and number of medications by ATC code, FAS

ATC code	ATC text	Sculptra N = XX		Control N = XX		
		Subjects		Number of medications	Subjects	
		n	%		n	%
	Total					

$\% = (n/N) * 100$

Note: A single subject may have reported several types of concomitant medication

Concomitant procedures

In a similar way as for conmed

Efficacy

Table 3-19: MMVS responder rate at Month 12 by treatment (both sides of the face combined), Blinded Evaluator

Population	Visit	Treatment	Subjects		Responders		95% Confidence interval			p-value
			N	n	n	%				
FAS ¹⁾	Month 12	Sculptra								
		Control								
		Difference								
PP ²⁾	Month 12	Sculptra								
		Control								
		Difference								
FAS ³⁾	Month 12	Sculptra								
		Control								
		Difference								

1) Note: Missing values at Month 12 are imputed using the BOCF method.

2) No imputation is used for PP analysis. Only subjects with complete data are included.

3) Note: Missing values at Month 12 are imputed using the Hot deck imputation method.

Note: Responder is defined as a subject with an improvement of at least one grade on the MMVS from baseline

Note: Responder rate (%) = $(n/N) * 100$

Note: P-values for the difference in proportions are based on the Fisher's Exact test.

Note: 95% confidence intervals are two-sided and calculated using the exact interval. For the difference, asymptotic confidence limits are used.

 GALDERMA	Title 43CHSA1803 Statistical Analysis Plan - Sculptra China	Doc id MA-40407
--	---	---------------------------

2019-10-24 08:59

Effective date:

Effective

Version: 1.0

Table 3-20: MMVS responder rate over time (both sides of the face combined), Blinded Evaluator, FAS, OC

Visit	Treatment	Subjects	Responders			95% Confidence interval			p-value
			N	n	%				
Month 6	Sculptra								
	Control								
	Difference								
Month 9	Sculptra								
	Control								
	Difference								
Month 12	Sculptra								
	Control								
	Difference								
Month 18	Sculptra								
Month 24	Sculptra								

Note: Responder is defined as a subject with an improvement of at least one grade on the MMVS from baseline.

Note: Responder rate (%) = $(n/N) * 100$

Note: P-values for the difference in proportions are based on the Fisher's Exact test.

Note: 95% confidence intervals are two-sided and calculated using the exact interval. For the difference, asymptotic confidence limits are used.

Note: The main study consists of visits up to 12 months

Figure 3-1: MMVS responder rate over time (both sides of the face combined), Blinded Evaluator, FAS, OC

Effective date: 2019-10-24 08:59

Effective

Version: 1.0

Table 3-21: MMVS over time, Blinded Evaluator, FAS, OC

Visit / Treatment			Side	MMVS								
				1 – Fairly full		2 – Mild loss		3 – Moderate loss		4 – Substantial loss		Total
Baseline	Sculptra	Left		n	%	n	%	n	%	n	%	N
		Right										
Month 6	Sculptra	Control	Left									
		Right										
	Control	Left										
		Right										
Month 9	Sculptra	Left										
		Right										
	Control	Left										
		Right										
Month 12	Sculptra	Left										
		Right										
	Control	Left										
		Right										
Month 18	Sculptra	Left										
		Right										
Month 24	Sculptra	Left										
		Right										

% = (n/N)*100

Note: The main study consists of visits up to 12 months

Table 3-22: MMVS responder rate over time (both sides of the face combined), Treating Investigator, FAS, OC

Same as for Blinded Evaluator

Figure 3-2: MMVS responder rate over time (both sides of the face combined), Blinded Evaluator, FAS, OC**Table 3-23: MMVS over time, Treating Investigator, FAS, OC**

Same as for Blinded Evaluator

	Title 43CHSA1803 Statistical Analysis Plan - Sculptra China	Doc id MA-40407
--	---	---------------------------

Effective date: 2019-10-24 08:59

Table 3-24: Volume change (mL) over time (both sides of the face combined) as measured by digital 3D photography, FAS

Visit / Treatment		N	Mean	SD	Median	Minimum	Maximum
Month 6	Sculptra						
	Control						
Month 9	Sculptra						
	Control						
Month 12	Sculptra						
	Control						
Month 18	Sculptra						
Month 24	Sculptra						

Note: The main study consists of visits up to 12 months

Table 3-25: GAIS responder rate over time, (both sides of the face combined), Treating Investigator, FAS, OC

Visit	Treatment	Subjects	Responders		95% Confidence interval
			N	n	
Month 6	Sculptra				
	Control				
Month 9	Sculptra				
	Control				
Month 12	Sculptra				
	Control				
Month 18	Sculptra				
Month 24	Sculptra				

Note: Subjects with a GAIS rating of 'Very much improved', 'Much improved', or 'Improved' are defined as responders.

Note: Responder rate (%) = $(n/N) * 100$

Note: 95% Confidence Intervals are two-sided confidence intervals calculated using the exact interval.

Note: The main study consists of visits up to 12 months

Figure 3-3: GAIS responder rate over time, (both sides of the face combined), Treating Investigator, FAS, OC

 GALDERMA	Title 43CHSA1803 Statistical Analysis Plan - Sculptra China	Doc id MA-40407
--	---	---------------------------

Effective date: 2019-10-24 08:59

Effective

Version: 1.0

Table 3-26: GAIS over time, Treating Investigator, FAS, OC

		GAIS										
Visit / Treatment	Side	Very much improved		Much improved		Improved		No change		Worse		Total
		n	%	n	%	n	%	n	%	n	%	
Month 6 Sculptra	Left											
	Right											
Control	Left											
	Right											
Month 9 Sculptra	Left											
	Right											
Control	Left											
	Right											
Month 12 Sculptra	Left											
	Right											
Control	Left											
	Right											
Month 18 Sculptra	Left											
	Right											
Month 24 Sculptra	Left											
	Right											

 $\% = (n/N)*100$

Note: The main study consists of visits up to 12 months

Table 3-27: GAIS responder rate over time (both sides of the face combined), Subject assessment, FAS, OC

Same as for Treating Investigator

Figure 3-4: GAIS responder rate over time, (both sides of the face combined), Subject assessment, FAS, OC**Table 3-28: GAIS over time, Subject assessment, FAS, OC**

Same as for Treating Investigator

2019-10-24 08:59

Effective date:

Effective

Version: 1.0

Table 3-29: Subject Satisfaction Questionnaire, Question 1), Subjects randomized to Sculptra, FAS, OC

Do you think your Cheek Volume deficit and/or Contour Deficiency has been improved with the treatment?					
Visit (after baseline)	Yes		No		Total
	n	%	n	%	N
Month 6					
Month 9					
Month 12					
Month 18					
Month 24					

% = (n/N)*100

Note: The main study consists of visits up to 12 months

Table 3-30: Subject Satisfaction Questionnaire, Question 2), Subjects randomized to Sculptra, FAS, OC

Do you think that the overall result of the treatment looks natural?					
Visit (after baseline)	Yes		No		Total
	n	%	n	%	N
Month 6					
Month 9					
Month 12					
Month 18					
Month 24					

% = (n/N)*100

Note: The main study consists of visits up to 12 months

Table 3-31: Subject Satisfaction Questionnaire, Question 3), Subjects randomized to Sculptra, FAS, OC

Would you say that the study treatment:									
Visit (after baseline)	Surpass your expectations		Meet your expectations		Do not meet your expectations		You did not have any specific expectations before the injections		Total
	n	%	n	%	n	%	n	%	
Month 6									
Month 9									
Month 12									
Month 18									
Month 24									

% = (n/N)*100

 GALDERMA	Title 43CHSA1803 Statistical Analysis Plan - Sculptra China	Doc id MA-40407
--	---	---------------------------

2019-10-24 08:59

Effective date:

Effective

Version: 1.0

Note: The main study consists of visits up to 12 months

Table 3-32: Subject Satisfaction Questionnaire, Question 4), Subjects randomized to Sculptra, FAS, OC

Visit (after baseline)	Do you think that the treatment brings you more:											
	Youth		Beauty		Harmony		Symmetrical appearance		Pep/Liveliness / Freshened look		Self-esteem/ confidence	
	n	%	n	%	n	%	n	%	n	%	n	%
Month 6												
Month 9												
Month 12												
Month 18												
Month 24												

% = (n/N)*100 where N=number of filled in questionnaires

Note: All that applies are ticked

Note: The main study consists of visits up to 12 months

Table 3-33: Subject Satisfaction Questionnaire, Question 5), Subjects randomized to Sculptra, FAS, OC

Visit (after baseline)	Would you say that you feel more attractive?							
	Yes		No		Total		N	
	n	%	n	%	n			
Month 6								
Month 9								
Month 12								
Month 18								
Month 24								

% = (n/N)*100

Note: The main study consists of visits up to 12 months

2019-10-24 08:59

Effective date:

Effective

Version: 1.0

Table 3-34: Subject Satisfaction Questionnaire, Question 6), Subjects randomized to Sculptra, FAS, OC

How do you feel about yourself since the treatment was performed?											
Visit (after baseline)	Very much better		Much better		Somewhat better		The same		Worse		Total
	n	%	n	%	n	%	n	%	n	%	
Month 6											
Month 9											
Month 12											
Month 18											
Month 24											

% = (n/N)*100

Note: The main study consists of visits up to 12 months

Table 3-35: Subject Satisfaction Questionnaire, Question 7), Subjects randomized to Sculptra, FAS, OC

Overall, how satisfied are you with the treatment result?									
Visit (after baseline)	Very satisfied		Satisfied		Somewhat satisfied		Not satisfied		Total
	n	%	n	%	n	%	n	%	
Month 6									
Month 9									
Month 12									
Month 18									
Month 24									

% = (n/N)*100

Note: The main study consists of visits up to 12 months

Table 3-36: Subject Satisfaction Questionnaire, Question 8), Subjects randomized to Sculptra, FAS, OC

Did you get any feedback about your look from your family, friends and colleagues?							
Visit (after baseline)	Positive feedback		Negative feedback		No feedback		Total
	n	%	n	%	n	%	
Month 6							
Month 9							
Month 12							
Month 18							
Month 24							

% = (n/N)*100

Note: The main study consists of visits up to 12 months

2019-10-24 08:59

Effective date:

Effective

Version: 1.0

Table 3-37: Subject Satisfaction Questionnaire, Question 9), Subjects randomized to Sculptra, FAS, OC

Visit (after baseline)	Yes		No		Total
	n	%	n	%	
Month 6					
Month 9					
Month 12					
Month 18					
Month 24					

% = (n/N)*100

Note: The main study consists of visits up to 12 months

Table 3-38: Subject Satisfaction Questionnaire, Question 10), Subjects randomized to Sculptra, FAS, OC

Visit (after baseline)	Yes		No		Total
	n	%	n	%	
Month 6					
Month 9					
Month 12					
Month 18					
Month 24					

% = (n/N)*100

Note: The main study consists of visits up to 12 months

2019-10-24 08:59

Effective date:

Effective

Version: 1.0

Treatment procedure**Table 3-39: Volume injected (both cheeks combined), Subjects randomized to Sculptra, Safety population**

Volume injected (mL)						
Visit	N	Mean	SD	Median	Minimum	Maximum
Baseline / Treatment 1						
Treatment 2 (optional)						
Treatment 3 (optional)						
Treatment 4 (optional)						
Total exposure						

Table 3-40: Treatment procedure (both cheeks combined, all treatments combined), Subjects randomized to Sculptra, Safety population

Characteristic	Answer	Statistic	Result
Was 1 ml of lidocaine added to the vial before treatment?	Yes	n (%)	
	No	n (%)	
Local anaesthesia used?	Yes	n (%)	
	No	n (%)	
If local anaesthesia used	Topical cream	n (%)	
	Local infiltration	n (%)	
Needle gauge	25 G	n (%)	
	26 G	n (%)	
Depth of injection	Deep dermis	n (%)	
	Subcutaneous layer	n (%)	
	Supraperiosteal layer	n (%)	
	Other	n (%)	
Primary injection method	Linear Retrograde	n (%)	
	Serial Puncture	n (%)	
	Fanning	n (%)	
	Other	n (%)	
Post-treatment care (ice and massage) according to study protocol?	Yes	n (%)	
	No	n (%)	
Any deviation from the treatment procedure as	Yes	n (%)	

Effective date: 2019-10-24 08:59

Effective

Version: 1.0

Characteristic	Answer	Statistic	Result
described in the study protocol?			
	No	n (%)	

List deviations:....

Table 3-41: Treatment procedure (both cheeks combined), Subjects randomized to Sculptra, Safety population

Characteristic	Visit	Statistic	Answer	Result
Was 1 ml of lidocaine added to the vial before treatment?	Baseline / Treatment 1	n (%)	Yes	
		n (%)	No	
	Treatment 2 (optional)	n (%)	Yes	
		n (%)	No	
	Treatment 3 (optional)	n (%)	Yes	
		n (%)	No	
	Treatment 4 (optional)	n (%)	Yes	
		n (%)	No	
Local anaesthesia used?	Baseline / Treatment 1	n (%)	Yes	
		n (%)	No	
	Treatment 2 (optional)	n (%)	Yes	
		n (%)	No	
	Treatment 3 (optional)	n (%)	Yes	
		n (%)	No	
	Treatment 4 (optional)	n (%)	Yes	
		n (%)	No	
If local anaesthesia used	Baseline / Treatment 1	n (%)	Topical cream	
		n (%)	Local infiltration	
	Treatment 2 (optional)	n (%)	Topical cream	
		n (%)	Local infiltration	
	Treatment 3 (optional)	n (%)	Topical cream	
		n (%)	Local infiltration	
	Treatment 4 (optional)	n (%)	Topical cream	
		n (%)	Local infiltration	
Needle gauge	Baseline / Treatment 1	n (%)	25 G	
		n (%)	26 G	

2019-10-24 08:59

Effective date:

Effective

Version: 1.0

Characteristic	Visit	Statistic	Answer	Result
	Treatment 2 (optional)	n (%)	25 G	
		n (%)	26 G	
	Treatment 3 (optional)	n (%)	25 G	
		n (%)	26 G	
	Treatment 4 (optional)	n (%)	25 G	
		n (%)	26 G	
Depth of injection	Baseline / Treatment 1	n (%)	Deep dermis	
		n (%)	Subcutaneous layer	
		n (%)	Supraperiosteal layer	
		n (%)	Other	
	Treatment 2 (optional)	n (%)	Deep dermis	
		n (%)	Subcutaneous layer	
		n (%)	Supraperiosteal layer	
		n (%)	Other	
	Treatment 3 (optional)	n (%)	Deep dermis	
		n (%)	Subcutaneous layer	
		n (%)	Supraperiosteal layer	
		n (%)	Other	
	Treatment 4 (optional)	n (%)	Deep dermis	
		n (%)	Subcutaneous layer	
		n (%)	Supraperiosteal layer	
		n (%)	Other	
Primary injection method	Baseline / Treatment 1	n (%)	Linear Retrograde	
		n (%)	Serial Puncture	
		n (%)	Fanning	
		n (%)	Other	
	Treatment 2 (optional)	n (%)	Linear Retrograde	
		n (%)	Serial Puncture	
		n (%)	Fanning	
		n (%)	Other	
	Treatment 3 (optional)	n (%)	Linear Retrograde	
		n (%)	Serial Puncture	

2019-10-24 08:59

Effective date:

Effective

Version: 1.0

Characteristic	Visit	Statistic	Answer	Result
		n (%)	Fanning	
		n (%)	Other	
	Treatment 4 (optional)	n (%)	Linear Retrograde	
		n (%)	Serial Puncture	
		n (%)	Fanning	
		n (%)	Other	
Post-treatment care (ice and massage) according to study protocol?	Baseline / Treatment 1	n (%)	Yes	
		n (%)	No	
	Treatment 2 (optional)	n (%)	Yes	
		n (%)	No	
	Treatment 3 (optional)	n (%)	Yes	
		n (%)	No	
	Treatment 4 (optional)	n (%)	Yes	
		n (%)	No	
Any deviation from the treatment procedure as described in the study protocol?	Baseline / Treatment 1	n (%)	Yes	
		n (%)	No	
	Treatment 2 (optional)	n (%)	Yes	
		n (%)	No	
	Treatment 3 (optional)	n (%)	Yes	
		n (%)	No	
	Treatment 4 (optional)	n (%)	Yes	
		n (%)	No	

List deviations:...

2019-10-24 08:59

Effective date:

Effective

Version: 1.0

Safety**Table 3-42: Anticipated injection related reactions recorded in the subject diary after first treatment (both sides of the face combined), Safety population**

Event	Treatment with Sculptra N=XX							
	Subjects		Maximum intensity					
			Mild		Moderate		Severe	
	n	%	n	%	n	%	n	%
Pain								
Tenderness								
Localized redness								
Bruising								
Hematoma								
Edema								
Other								
No diary events								

 $\% = (n/N)*100$

Note: Percentages for intensity categories are based on the number of subjects reporting the symptom.

Table 3-43: Number of days anticipated injection related reactions recorded in subject diary after first treatment (both sides of the face combined), Safety population

Event	Treatment with Sculptra N=XX					
	n	Mean	SD	Minimum	Median	Maximum
Pain						
Tenderness						
Localized redness						
Bruising						
Hematoma						
Edema						
Other						

Figure 3-5: Proportion of subjects with observed anticipated injection related reactions (to any intensity level) after first treatment with Sculptra (both sides of the face combined), Safety population

Same tables and figure for treatment sessions two, three and four

 GALDERMA	Title 43CHSA1803 Statistical Analysis Plan - Sculptra China	Doc id MA-40407
--	---	---------------------------

Effective date: 2019-10-24 08:59

Table 3-44: Brief summary of all AEs, Main study, Safety population

	Sculptra, N=XX			Control, N=YY		
	Subjects		Events	Subjects		Events
	n	%	#	n	%	#
Adverse Events reported, total						
Total, serious						
Total, non-serious						
AEs related to injection procedure and/or product, total						
Serious						
Non-serious						
Unrelated AEs, total						
Serious						
Non-serious						
Subjects with no AE reported						

$$\% = (n/N) * 100$$
Table 3-45: Related Adverse Events by MedDRA SOC and preferred term, Main study, subjects randomized to Sculptra, Safety population

Primary SOC	Preferred Term	Subjects		Events	Maximal Intensity		
		n	%		Mild	Moderate	Severe
Total							

$$\% = (n/number of subjects in the Safety population) * 100$$
Effective

Version: 1.0

	Title 43CHSA1803 Statistical Analysis Plan - Sculptra China	Doc id MA-40407
--	---	---------------------------

**Table 3-46: Related Adverse Events by MedDRA SOC and preferred term, by treatment session,
Main study, subjects randomized to Sculptra, Safety population**

Visit	Primary SOC	Preferred Term	Subjects		Events #	Maximal Intensity		
			n	%		Mild	Moderate	Severe
Baseline / Treatment 1								
Treatment 2 (optional)								
Treatment 3 (optional)								
Treatment 4 (optional)								

% = (n/number of subjects in the Safety population)*100

2019-10-24 08:59

Effective date:

Effective

Version: 1.0

**Table 3-47: Time to onset from last treatment of related AEs,
Main study, subjects randomized to Sculptra, Safety population**

Preferred term	Time to onset (days)					
	n	Mean	SD	Min	Median	Max
Total						

NA = Not Applicable

**Table 3-48: Duration of related AEs,
Main study, subjects randomized to Sculptra, Safety population**

Preferred term	Duration (days)					
	n	Mean	SD	Min	Median	Max
Total						

NA = Not Applicable

**Table 3-49: Action taken of related AEs,
Main study, subjects randomized to Sculptra, Safety population**

Preferred term	Action taken			
	None	Medication treatment	Non-pharmacological treatment or other procedures / tests	Withdrawn
Total				

**Table 3-50: Unrelated Adverse Events by MedDRA SOC and preferred term,
Main study, Subjects randomized to Sculptra, Safety population**

Primary SOC	Preferred Term	Subjects		Events #	Maximal Intensity		
		n	%		Mild	Moderate	Severe
Total							

% = (n/number of subjects in the Safety population)*100

 GALDERMA	Title 43CHSA1803 Statistical Analysis Plan - Sculptra China	Doc id MA-40407
--	---	---------------------------

2019-10-24 08:59

Effective date:

**Table 3-51: Unrelated Adverse Events by MedDRA SOC and preferred term,
Main study, Subjects randomized to no-treatment control, Safety population**

Primary SOC	Preferred Term	Subjects		Events #	Maximal Intensity		
		n	%		Mild	Moderate	Severe
Total							

% = (n/number of subjects in the Safety population)*100

AE tables for Extension phase

Same tables as above when applicable

AE tables for Combined phases

Same tables as above when applicable

Group A

The same tables as for Group B, when applicable

Effective

Version: 1.0

	
Title 43CHSA1803 Statistical Analysis Plan - Sculptra China
	
Doc id MA-40407

--	--	-----------------------------------

2019-10-24 08:59

Effective date:

Effective

Version: 1.0

SIGNATURES PAGE

Date	Signed by
2019-10-23 07:15	[Redacted]
Justification	Approved by Owner
2019-10-23 08:02	[Redacted]
Justification	Approved by Technical Expert
2019-10-23 08:29	PPD [Redacted]
Justification	Approved by Technical Expert
2019-10-24 08:59	[Redacted]
Justification	Approved by Technical Expert

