2.2 Analysis Populations

The following populations will be defined:

- Safety
- Includes all subjects in Group B who were treated with Sculptra or randomized to no-treatment group. Subjects are analyzed based on the as treated principle.
- Full Analysis Set (FAS)
- Includes all subjects in Group B who were treated with Sculptra or randomized to no-treatment group. Subjects are analyzed according to the randomisation assignment.
- Per Protocol (PP)
- Includes all subjects in FAS that comply to the protocol procedures with no deviations that can affect the evaluation of the primary variable.

The FAS population is the primary population for all effectiveness analyses. All safety analyses will be based on the Safety population.

For Group A, all analyses will be performed based on all subjects.

 GALDERMA	Title 43CHSA1803 Statistical Analysis Plan - Sculptra China	Doc id MA-40407
--	---	---------------------------

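### Exposure tables and detailed related-AE tables select on randomized arm although the Safety set is analysed as treated, so they would omit a Control subject injected in error

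*SAP*

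**What the plan says.** SAP 2.2 defines the Safety set as follows: "Includes all subjects in Group B who were treated with Sculptra or randomized to no-treatment group". It then fixes the grouping rule, "Subjects are analyzed based on the as treated principle", and the scope, "All safety analyses will be based on the Safety population".

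The table shells in SAP section 3 do not all follow that rule.

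- Table 3-39 is titled "Volume injected (both cheeks combined), Subjects randomized to Sculptra, Safety population". Tables 3-40 and 3-41 (treatment procedure) also end in "Subjects randomized to Sculptra, Safety population".
- Tables 3-45 to 3-49 cover related AEs by SOC and preferred term, by session, time to onset, duration and action taken. All five carry "Main study, subjects randomized to Sculptra, Safety population".
- Tables 3-50 and 3-51 present unrelated AEs, one for each randomized arm.
- "Table 3-44: Brief summary of all AEs, Main study, Safety population" has Sculptra and Control columns and no restriction by randomization. Its rows include "AEs related to injection procedure and/or product, total".

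The SAP text behind these shells does not restrict by randomized arm. SAP 2.5.1 (exposure) and 2.5.3 (adverse events) are silent on it, SAP 2.5.2 limits the diary summary to subjects who received Sculptra, and protocol 10.5 asks for the related-AE summaries by treatment.

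**The concern.** An as-treated rule exists for subjects whose actual treatment differs from their assignment. In Group B it can change the grouping in only one way. A subject randomized to Sculptra who is never injected is outside the Safety set by definition, which leaves only a Control subject who receives Sculptra. A selection on subjects randomized to Sculptra excludes exactly that subject, so in the eight tables concerned the as-treated rule has no effect.

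The detailed tabulation of that subject's exposure and related events would be lost. This matters most for non-serious related events, because serious AEs are listed individually in any case. Papules and nodules are recorded as AEs (protocol 8.3.3), and protocol 8.3.8 anticipates late onset and long duration for nodules. The onset, duration and action-taken tables are therefore the ones that describe the product's characteristic reactions.

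**Working it through.** The plan states no figure on this point, so the check is mainly a comparison of the text.

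**Step 1: trace one Control subject injected in error.** The subject is in the Safety set and, as treated, belongs with Sculptra.

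| Output | Selection stated | What happens to this subject |
|---|---|---|
| Tables 3-39 to 3-41, exposure and procedure | Randomized to Sculptra | Omitted |
| Tables 3-42 and 3-43, diary | Sculptra treatment received | Included, if a diary was kept |
| Table 3-44, AE summary | Safety population, no arm restriction | Counted, in the Sculptra column |
| Tables 3-45 to 3-49, related AEs | Randomized to Sculptra | Omitted |
| Table 3-50, unrelated AEs | Randomized to Sculptra | Omitted |
| Table 3-51, unrelated AEs | Randomized to Control | Unrelated AEs shown here as Control events |
| Serious and late-onset AE listings (SAP 2.5.3), subject listings (SAP 2.1) | No arm restriction | Shown |

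The subject is therefore lost from 3 + 5 = 8 tables. For unrelated AEs the subject is misplaced, not lost.

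**Step 2: reconciliation.** With one such subject, the Sculptra column of Table 3-44 contains one more subject, and any related events of that subject, than Tables 3-45 to 3-49 can account for.

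**Step 3: size.** Inputs: 126 subjects planned for Sculptra (SAP 2.7), all assumed to be treated; m = number of Control subjects injected in error, which the documents do not give and which is assumed here to be 0 to 3.

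Share of exposed subjects omitted = m / (126 + m):

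- m = 0: 0 / 126 = 0%
- m = 1: 1 / 127 = 0.8%
- m = 2: 2 / 128 = 1.6%
- m = 3: 3 / 129 = 2.3%

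**Step 4: does the selection matter without an error?** No. If no Control subject is injected, Safety-set subjects randomized to Sculptra and Safety-set subjects treated with Sculptra are the same people.

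**Step 5: scope beyond the main phase.** The end of SAP section 3 reuses the same AE tables, where applicable, for the extension and combined phases, so the selection would be carried forward.

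**The case against.** The strongest defence is that the governing text is sound. SAP 2.2 states the as-treated rule, SAP 2.5 repeats the Safety population, and the conflict appears only in the titles of empty shells that also name that population. On this view it is loose labelling, not a decision to analyse by randomized arm. The error is also improbable. Treating investigator and subject both know the assignment (protocol 4.4.2), and the Control schedule has no treatment visits and nothing between baseline and Month 6. A mis-injection would mean an unblinded injector treating a subject known to be assigned to no treatment.

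The argument about probability stands and limits the importance of the point. The labelling argument stands only in part. Shells are what programmers work from, and these state a selection that contradicts the rule, while the diary shells follow treatment received.

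Two stronger readings are tempting, and the documents support neither. A reader might infer that the injected subject's related events would vanish from every related-AE output. They would not: Table 3-44 has related-AE rows and no arm restriction, and the serious, late-onset and subject listings are unrestricted too. A reader might also infer from SAP Table 3, which names treatment at odds with randomization, that such errors are expected. That table only lists deviations that exclude a subject from the per-protocol set. It neither predicts their occurrence nor singles out injected Controls.

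**Conclusion.** The point holds as a minor inconsistency. The titles of Tables 3-39 to 3-41 and 3-45 to 3-51 select on randomized arm and so contradict SAP 2.2 in the one Group B situation where its as-treated rule has any effect. The harm is confined to incomplete exposure and detailed related-AE tables, unrelated AEs attributed to the wrong group, and a mismatch with Table 3-44.

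The size depends on an error that may never occur. The 0.8% to 2.3% range rests on two assumptions: one to three mis-treated Controls, and treatment of all 126 subjects randomized to Sculptra. The primary analysis, the sample size and all effectiveness inference are untouched.

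**What to change.** - Select and title Tables 3-39 to 3-41 and 3-45 to 3-50 on *subjects treated with Sculptra*.
- Select and title Table 3-51 on *subjects not treated with Sculptra*.
- Carry the same selection into the extension-phase and combined-phase AE tables.
- Leave Tables 3-42 to 3-44 as they are, since they already fit the as-treated rule.

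The cost is a set of table titles and one selection variable in the programs. No data collection or inference changes. SAP 2.1 provides for amending the SAP before database lock, so the change can be made by that route.
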